18.6. Reporting and timelines

18.6.1. Investigator's reporting responsibilities

- PI at each site must assess all (S)AE's that occur at his/her site.
- All serious adverse events and serious adverse device effects must be reported to sponsor within 24 hours of the site becoming aware of the event.
- A device deficiency that could have led to a serious adverse event but did not because suitable action was taken, intervention had been made or because of fortunate circumstances should be reported to sponsor within 24 hours of the site becoming aware of the event.
- New findings and/or updates in relation to already reported serious events should also be reported to sponsor within 24 hours of the site becoming aware of the event.
- *Device deficiencies and all adverse device effects related to Coloplast investigational product and/or comparator must be reported to sponsor within 24 hours of becoming aware of the event.*

When reporting the SAE, the relationship to the test material shall be described whether the event is considered

- **Not related**, the event has no temporal relationship with the use of the test material or the procedures.
- **Unlikely related**, the relationship with the use of the test material seems not relevant and/or the event can be reasonably explained by another cause, but additional information may be obtained.
- **Possible related**, the relationship with the use of the test material is weak but cannot be ruled out completely. Alternative causes are also possible (e.g. an underlying or concurrent illness/ clinical condition or/and an effect of another device, drug or treatment). Cases where relatedness cannot be assessed or no information has been obtained should also be classified as possible.
- **Probable related**, the relationship with the use of the test material seems relevant and/or the event cannot reasonably be explained by another cause, but additional information may be obtained.
- **Definitely related/Causal relationship**, the event has a temporal relationship with the test material use/application or procedures.

and the intensity of the event should be considered, as such:

- **Mild**, the intensity of the event is mild with no further action or intervention
- **Moderate**, the intensity of the event will lead to an action or intervention to solve the event
- **Severe**, the intensity of the event will lead to follow up on the action or intervention, as the effect of the action or intervention may not decrease the symptoms.

All above events must be reported by use of the relevant adverse event/serious adverse event/device deficiency form.

Please report to:

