3.1. Objective (s)

Primary objective: To demonstrate superiority of the new compact catheter in terms of improved bladder emptying, with the catheterization performed by a health care professional.

Secondary objective: Is to assess safety of the new compact catheter in support of the CE marking

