18.1. Adverse events

An adverse event is any untoward medical occurrence, unintended disease or injury, or untoward clinical signs (including abnormal laboratory findings) in subjects, whether or not related to the investigational medical device(s) or the comparator(s), or the procedures involved. The adverse event shall be marked with the intensity mild, moderate or severe. This could include events such as headache or dizziness.

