18.2. Adverse device effect

An adverse event, which is related to the use of the investigational medical device (including comparator), is an adverse device effect, and should be marked as unlikely related, possible related, probable related or with causal relationship on the adverse event form.

The definition of an adverse device effect includes any event resulting from insufficiencies or inadequacies in the instruction for use, *deployment*, or any malfunction of the medical device, as well as any event resulting from use error or from intentional misuse of the device.

Table 1 lists anticipated adverse device effects that may occur.

Table 1 Anticipated adverse device effects and their likely incidence rates

ANTICIPATED ADE	INCIDENCE RATE
Irritation of mucosa	Likely
Stinging and pain in urethra during catheterisation	Likely
Macroscopic haematuria	Unlikely
Macroscopic leukocytes	Unlikely
Urinary tract infection	Very unlikely

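### AE intensity grades in 18.6.1 rest on the action taken, so intense pain that resolves unaided has no valid grade and will tend to be recorded as Mild

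*Combined protocol and SAP*

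**What the plan says.** Section 18.1 sets the requirement: "The adverse event shall be marked with the intensity mild, moderate or severe". It does not define the three words.

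The definitions come in 18.6.1. Mild means "the intensity of the event is mild with no further action or intervention". Moderate means "the intensity of the event will lead to an action or intervention to solve the event". Severe means "the intensity of the event will lead to follow up on the action or intervention", with the added reason that the action may fail to relieve the symptoms.

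These lines belong to a block that opens "When reporting the SAE, the relationship to the test material shall be described whether the event is considered", which names serious events only. The block closes more widely: "All above events must be reported by use of the relevant adverse event/serious adverse event/device deficiency form".

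The table of anticipated device effects in 18.2 lists "Stinging and pain in urethra during catheterisation" with the incidence label Likely. The secondary objective in 3.1 reads "Is to assess safety of the new compact catheter in support of the CE marking". Section 10.1 (statistical design) says this objective is evaluated through adverse events and discomfort.

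**The concern.** An intensity grade should tell the reader how bad the event was for the subject. Two of these three grades instead tell the reader what staff did next, and the third adds an absence of action to a circular statement.

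This matters here because urethral stinging and pain is an expected device effect, the catheter is in place for less than 60 minutes (4.3), and such pain can plausibly end without anyone doing anything. A catheter that hurts more on insertion might then show no difference in recorded AE intensity. A statement in the clinical investigation report that device-related events were mild would partly restate that no action was taken. That is weak support for a safety objective tied to CE marking.

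**Working it through.** No arithmetic applies to the grading rule, so the check is to apply the definitions as written.

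**Step 1. Conditions in each grade (18.6.1).**
- Mild: the intensity is mild, and there is no further action. Both are needed.
- Moderate: an action or intervention follows.
- Severe: the action is followed up, because it may not relieve the symptoms.

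No grade describes how tolerable the symptom is or whether it interferes with anything the subject does.

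**Step 2. Cross intensity with management.**

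| Management that follows | Low symptom intensity | High symptom intensity |
|---|---|---|
| None | Mild | No grade fits |
| Action | Moderate | Moderate |
| Action, followed up because relief is doubtful | Severe | Severe |

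In the first row, the high-intensity event fails Mild (its intensity is not mild), fails Moderate (no action) and fails Severe (no action to follow up). The site must still enter a grade, and the only one compatible with no action is Mild. In the second and third rows the grade is the same in both columns, so it carries information about management only. The wording does say that the intensity leads to the action, but it gives no level of intensity that would separate the columns.

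**Step 3. Scope.** Two readings are possible.
- If the grades apply to all AEs, as 18.1 and the closing sentence about forms suggest, the gap in Step 2 reaches the expected non-serious events.
- If they apply only to SAEs, as the opening sentence says, non-serious stinging must be graded under 18.1 with no definition at all.

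Either reading needs correcting.

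**Step 4. Is pain intensity captured elsewhere?** Sections 5.4 and 7.2 place the 10 cm VAS with the self-catheterisation, which is done at Danish sites only, once per subject, at Visit 2. One self-catheterisation per subject gives no within-subject comparison of devices. The HCP catheterisations number 72 subjects × 2 devices = 144 (4.6 gives the same total), and the flow-chart in 7.3 schedules no pain or discomfort scale for them. For those 144, the AE intensity grade is the only planned record of how intense any pain was.

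**Step 5. What depends on the grade?** The safety endpoint in 5.3 is the number of adverse events, which is the same under any intensity definition. Section 10.5 plans listings or summaries and names no analysis by intensity. The pass/fail rule uses the primary endpoint alone. The effect is therefore confined to the intensity field, to any listing or summary that shows it, and to text written from it.

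**The case against.** The strongest reply is that little hangs on this field. No severity profile is a planned endpoint or analysis, the AE count does not change, seriousness is defined separately in 18.4, and the 24-hour reporting of device effects does not depend on intensity. All of that stands, and it limits the point to data quality in a descriptive field.

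A second reply is that Mild does require mild intensity, so on the text severe self-limiting pain is not Mild. That is correct. The defect is an event without a grade. That it will be coded Mild is a judgement about what sites will do with a mandatory field, not something the text orders.

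A third reply is that discomfort is measured directly by VAS and is named as part of the safety evaluation. This is a partial answer only, for the reason in Step 4.

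A reader might also infer three stronger things that the documents do not support:
- **That a treated and followed-up minor urinary tract infection becomes Severe.** The Severe definition ties follow-up to doubt about symptom relief, so an infection that responds to treatment fits Moderate.
- **That nearly all expected device events will be Mild whatever their true intensity.** Section 18.2 gives verbal labels without rates, and nothing in the protocol says how often such events need action. Section 8.1 asks that mild pain or bleeding be discussed with the investigator or designee, and whether that counts as an action is not defined.
- **That the safety evaluation is wrong by construction.** It rests on a count and on discomfort, neither of which uses these grades.

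**Conclusion.** The point holds in a limited form. The definitions in 18.6.1 leave intense events that resolve without action with no valid grade, and they grade a trivial event that prompts an action as Moderate. Their scope is also unclear, because 18.1 asks for a grade on every AE while the definitions are introduced for SAEs.

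The AE count, the sample size, the power and the primary conclusion are unaffected. Intensity as listed or summarised would partly reflect management, and so would any report statement that events were mild. The number of events affected is unknown and cannot be estimated from the documents.

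The conclusion assumes that the grades are used for non-serious AEs, and that the AE form and eCRF guidance, which are not part of the document, do not supply other definitions. If the grades are for SAEs only, the problem becomes a missing definition for all other AEs. With 8 sites in two countries, an event that fits no grade also invites inconsistent coding, and intensity that is not graded properly at the time is hard to recover later. The correction is worth making before enrolment starts.

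**What to change.** In 18.6.1, rewrite the three intensity lines so that each describes the symptom: how tolerable it is while it lasts, and interference with activities where that is relevant. Tolerability should come first, because interference with usual activities separates pain lasting seconds poorly.

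State in 18.1 and 18.6.1 that the grades apply to all AEs, serious or not. Record action taken and outcome as separate fields on the AE form, so that the information now folded into Moderate and Severe is kept.

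The cost is three definition lines, a scope sentence, and an update to the AE form, eCRF guidance and site training. It needs no extra visits or measurements and does not touch the primary analysis.

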18.6.2. Sponsors reporting responsibilities

It is the responsibility of sponsor to ensure that the following are reported to national regulatory authorities immediately, but no later than 7 calendar days following the date of awareness by sponsor.

- All serious adverse events.
- All serious device effects.
- All device deficiencies that could have led to serious adverse events but did not because suitable action was taken, intervention had been made or because of fortunate circumstances.
- New findings and/or updates in relation to already reported events.

If the serious adverse event results in imminent risk of death, serious injury, or serious illness that requires prompt remedial action for other subjects, users or other persons or a new finding to such a serious adverse event, sponsor must immediately but no later than 2 calendar days after awareness by sponsor report the event to *national regulatory authorities*.

It is the responsibility of sponsor to inform all investigators in writing within 10 working days if device deficiencies, adverse events, adverse device effects, near-incidents, serious adverse events, serious adverse device effects or unanticipated serious adverse device effects lead to corrective actions (e.g. change of IFU).

19. Suspension or premature termination of the clinical investigation

Sponsor may suspend or prematurely terminate an investigation site or the entire clinical investigation for documented significant reasons.

If a suspicion of an unacceptable risk to subjects develops during the clinical investigation, sponsor will suspend the investigation while the risk is assessed. Sponsor will terminate the investigation if an unacceptable risk is confirmed. Sponsor will ensure that the premature termination will be justified in writing and will promptly inform the regulatory authorities and relevant EC/IRB. If monitoring or auditing of the clinical investigation identifies serious or repeated deviations at one of the participating investigation sites, sponsor will suspend or terminate the particular investigational site. The sponsor or investigator will inform the regulatory authority as appropriate and notify the EC/IRB about the termination of the site.

20. Clinical investigation report

At completion of the investigation sponsor is responsible for writing the clinical investigation report. The report is retained on file. The report contains a critical evaluation of all data, which have been collected during the investigation. The report describes the methodology and design and a data analysis, including statistical preparation and conclusion.

Sponsor and national coordinating investigators must sign the final version of the clinical investigation report or an affidavit, indicating their agreement with the contents. If no coordinating investigators are appointed, then the signatures of the principal investigators should be obtained.

The clinical investigation report must be submitted to EC and regulatory authorities.

21. Publication policy

Coloplast, sponsor, is referring to the internal document 'Clinical Publication Policy' that will be available for internal and external persons involved in the publication process.

The investigation will be registered in a publicly accessible database before recruitment of the first subject. The results of the investigation, positive as well as inconclusive and negative will be published in the same publicly accessible database. The subjects' identity will remain confidential. Publication of results in the database will be conducted per the law of personal data protection and will be initiated as soon as scientifically acceptable, however, within one year after the last subject has completed the investigation. Data from the investigation is considered confidential until it is published per the conditions of this Clinical Investigation Plan and the 'Clinical Publication Policy'. Sponsor may publish anonymous single subject case stories (or public, if the subject consents) at any time during and after the investigation. The identification of the participant must not be possible. Sponsor reserves the right to use the data (published and unpublished) for reimbursement or regulatory purposes.

22. Suspension/termination of the clinical investigation

Sponsor will withdraw from sponsorship of the clinical investigation if

- major non-adherence to the clinical investigation plan is occurring
- it is anticipated that the subject recruitment will not be adequate to meet the investigation objectives at least 75% of the subjects should be entered within the recruitment time.

In case sponsor withdraws, sponsorship for the subjects already recruited into the clinical investigation will continue.

